8.4.5.2 Management of savolitinib-related toxicities

Potential savolitinib-related toxicities during the course of the study can be managed as medically indicated and with interruption of the dose of savolitinib or dose reductions as appropriate, **unless symptoms are associated with hypersensitivity** (see [Appendix I Section I 3](#)). Repeat dose interruptions are allowed as required, taking into consideration the additional precautions for restart of savolitinib as illustrated in [Appendix I](#). For each patient the savolitinib dose can be reduced a maximum of 2 times ([Table 9](#)). No dose re-escalations are allowed.

Dose modification guidelines for QTc prolongation are shown in [Table 12](#).

Table 12 Dose modifications for QTc prolongation

NCI CTCAE Toxicity Grade	Action with savolitinib	Action with osimertinib
Grade 0, 1, or 2	None	None
Grade 3 Patients with QTcF prolongation to >500 msec on at least 2 separate ECGs If the toxicity does not resolve to QTcF <481 msec within 21 days	Hold dosing and follow algorithm below: Consult with cardiologist to validate ECG finding. Ensure cardiac surveillance and take actions in accordance with clinical standards. Regular ECGs performed until resolution to QTcF <481 msec and then restart drug at one reduced dose level.* Permanently discontinue study drug and consult with a cardiologist for further management as clinically indicated.	Hold dosing and follow algorithm below: Withhold until QTc interval is <481 msec or recovery to baseline if baseline QTc is more than 481 msec within 21 days of onset, then restart at a reduced dose (40 mg) or at 80 mg (at the discretion of the investigator). Permanently discontinue osimertinib.
Grade 4 QTcF \geq 501 or >60 msecs change from baseline and Torsade de pointes or polymorphic ventricular tachycardia or signs/symptoms of serious arrhythmia	Permanently discontinue study drug and consult with a cardiologist for further management as clinically indicated.	Permanently discontinue osimertinib.

CTCAE Common Terminology Criteria for Adverse Events; ECG Electrocardiogram; NCI National Cancer Institute; QTc corrected QT interval; QTcF corrected QT interval using Fridericia's formulas.

***For French sites only**, as per ANSM advice, the patient must remain hospitalised with continuous cardiac monitoring (ECG) until specialist advice is obtained by a cardiologist.

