Grade 4 
 QTcF \geq501 or >60 msec change from baseline and Torsade de pointes or polymorphic ventricular tachycardia or signs/symptoms of serious arrhythmia 	
 Discontinue study drug and consult with a cardiologist for further management as clinically indicated

CTCAE Common Terminology Criteria for Adverse Events; ECG Electrocardiogram; NCI National Cancer Institute; QTcF corrected QT interval using Fridericia's formulas.

I 3.5 Guideline for the Management of Overlapping Toxicities Between Osimertinib and Savolitinib

QTc Prolongation

QT prolongation is a recognised toxicity of osimertinib and savolitinib; management of this toxicity is summarised in [Table 25](#).

Table 25 Management of QTc prolongation

CTCAE Grade	Instructions for osimertinib	Instructions for savolitinib	Further investigation required
CTCAE Grade 1 or Grade 2	
 No action required 	
 No action required 	
 Review concomitant treatments and comorbidities for risks of QT prolongation or risk for TdP^a
CTCAE Grade 3 (QTc interval >500 msec or >60 msec change from baseline on at least 2 separate ECGs)	
 Withhold osimertinib until QTcF interval is <481 msec within 21 days of onset, then restart osimertinib at a reduced dose of 40 mg. Dose may be resumed at 80 mg at the discretion of the investigator if the event of QTc interval is considered to be non-related to osimertinib treatment 	
 Withhold savolitinib until QTcF interval is <481 msec. If the QTcF resolves to <481 msec in 21 days, restart savolitinib at a reduced dose 	
 Review concomitant treatments and comorbidities for risks of QT prolongation or risk for TdP^a Consult with a cardiologist to validate ECG finding Ensure cardiac surveillance and take actions in accordance with clinical standards Regular ECGs performed until resolution to QTcF <481 msec

CTCAE Grade	Instructions for osimertinib	Instructions for savolitinib	Further investigation required

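### Tables 12 and 25 give different written Grade 3 QTc instructions for both drugs with no stated precedence, and Table 25's release limit can already be met when its >60 msec arm fires

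*Protocol*

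**What the plan says.** Two tables are each presented as the QTc guideline, and each has a column for osimertinib and a column for savolitinib.

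- Sections 8.4.5.1 and 8.4.5.2: "Dose modification guidelines for QTc prolongation are shown in" Table 12. Its Grade 3 line reads "Patients with QTcF prolongation to >500 msec on at least 2 separate ECGs". After recovery, the osimertinib column says "then restart at a reduced dose (40 mg) or at 80 mg (at the discretion of the investigator", with no causality condition. A change of >60 msec appears in Table 12 only in the Grade 4 row, joined to arrhythmia.
- Appendix I 3.5: "QT prolongation is a recognised toxicity of osimertinib and savolitinib; management of this toxicity is summarised in" Table 25. Its Grade 3 line reads "QTc interval >500 msec or >60 msec change from baseline on at least 2 separate ECGs". Osimertinib restarts at 40 mg, with one exception that turns on whether osimertinib was the cause: "Dose may be resumed at 80 mg at the discretion of the investigator if the event of QTc interval is considered to be non-related". For savolitinib the rule is "Withhold savolitinib until QTcF interval is <481 msec", followed by "If the QTcF resolves to <481 msec in 21 days, restart savolitinib at a reduced dose". Failure to get below 481 msec in 21 days means discontinuation of each drug.

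Section 6.6 and Section 2.3.1 refer to Appendix I as a whole. The one priority rule, at the start of Appendix I 1, puts the local label first. It covers osimertinib only and does not rank the tables.

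**The concern.** QTc prolongation is a known effect of both drugs, and Section 2.3.1 reports that savolitinib's thorough QT study was positive. The hold rule should therefore give one answer for one ECG. As written, a site that takes Table 12's line as the whole Grade 3 criterion could keep both drugs going on an ECG for which Table 25 withholds both. After an event of uncertain cause, one table leaves an 80 mg osimertinib restart open and the other does not.

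Table 25 also has a gap of its own. Its trigger has two arms, one absolute and one relative to baseline, but its only release limit is absolute. Where the relative arm fires at a low QTcF, the instruction to withhold has no content, yet the dose reduction still follows. Section 8.4.5 does not allow either dose to be raised again.

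**Working it through.** No sample-size or error-rate figure is involved, so the check compares the two texts and then works out where they part.

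**Inputs.** Table 12 trigger: QTcF >500 on two or more ECGs. Table 25 trigger: >500, or more than 60 above baseline, on two or more ECGs. Table 25 release limit: <481. Entry limits (Section 5.2, exclusion criterion 3): QTcF up to 450 for men and 470 for women. Whole msec throughout, two qualifying ECGs, no arrhythmia. Let b be the baseline and Q the on-treatment QTcF.

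**Step 1, where the written triggers differ.** Only Table 25 is met when b + 61 ≤ Q ≤ 500. The number of such values is 500 − (b + 61) + 1 = 440 − b, which is positive for b up to 439.

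**Step 2, where the release limit is already met at onset.** This needs b + 61 ≤ Q ≤ 480. The number of values is 480 − (b + 61) + 1 = 420 − b, which is positive for b up to 419.

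| Baseline | Only Table 25 met | Release limit already met |
|---|---|---|
| 380 | 441–500 (60 values) | 441–480 (40) |
| 400 | 461–500 (40) | 461–480 (20) |
| 419 | 480–500 (21) | 480 (1) |
| 420 | 481–500 (20) | none |
| 439 | 500 (1) | none |
| 440 or more | none | none |

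Baselines up to 439 lie inside the entry limits for both sexes. The counts are positions on a msec scale, not patients or probabilities.

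**Step 3, two examples.**

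- Baseline 420, QTcF 490: the change is 490 − 420 = 70, above 60, and 490 is not above 500. Table 12's written line is not met. Table 25 withholds both drugs, and the hold is real because 490 is not below 481.
- Baseline 400, QTcF 465: the change is 465 − 400 = 65, so Table 25 fires. But 465 is already below 481. Savolitinib goes to a reduced dose, and osimertinib to 40 mg unless the event is judged unrelated, without an effective hold.

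**Step 4, the 80 mg restart.** Table 12 sets no causality condition. Table 20 (Appendix I 1) gives the same discretion and explains it by the difficulty of judging causality. Table 25 requires a judgement that osimertinib was not the cause. The two agree when the event is clearly unrelated. They part for any other event that an investigator would be willing to restart at 80 mg.

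**The case against.** **Table 25 is the later and more specific guideline.** The version history lists Appendix I 3.5 as new in version 7.0, and the section is about toxicities shared by the two drugs. Tables 21 and 24 are titled for one drug each, so a reader who infers a five-way conflict goes too far; the conflict is between Tables 12 and 25. This is a good reason to let Table 25 govern. It is not a precedence statement, and Table 12 also instructs on both drugs. Section 8.4.5.2 does cite Appendix I Section I 3, but beside hypersensitivity wording.

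**The tables are indexed by CTCAE grade.** Table 12 says no action only for Grades 0 to 2. If an isolated >60 msec change is graded 3, a site should hold under Table 12 as well. This stands. A reader might infer that a site using Table 12 would necessarily continue both drugs, but the documents do not support that, because they do not reproduce the CTCAE definition. What remains is that Table 12's algorithm has no branch for the case.

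**The restart gap is narrow.** Section 8.3.5 requires a yes-or-no causality answer, both tables involve investigator discretion, and the local label comes first for osimertinib. This narrows the difference without removing it, given Table 20's own explanation.

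**Monitoring continues.** A reader might infer that ECG follow-up ends at 481 msec. Only the extra event-driven ECGs do; scheduled triplicate ECGs continue on Day 1 of every cycle (Table 1), and Table 25 adds cardiologist validation and cardiac surveillance. These limit the risk but set no other trigger or release limit.

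**Reduction without a hold may be sensible.** Appendix I 3.4 reports that acute hypersensitivity, including anaphylaxis, has occurred mostly when savolitinib was restarted. Avoiding an interruption at a QTcF below 481 msec could be deliberate. This stands as a clinical possibility, but the protocol does not say so.

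**Conclusion.** The point holds as a conflict of written instructions that bears on patient safety. Two tables cover the same event for the same two drugs, differ on the Grade 3 trigger (baselines up to 439 msec) and on the 80 mg osimertinib restart, and are not ranked. In addition, Table 25's release limit does not fit its own >60 msec arm for baselines up to 419 msec; at 420 to 439 it does.

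This rests on the tables as printed, whole-msec values and no accompanying arrhythmia. The documents give neither the distribution of baseline QTcF nor the frequency of such events, so the number of patients affected cannot be stated.

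Two further inferences are tempting. One is that a release limit relative to baseline is required; the documents do not settle that, since longer savolitinib holds carry their own risk. The other is that efficacy results are compromised; nothing here changes ORR, power or error rates.

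**What to change.** 1. State in Section 8.4.5 and in Appendix I that Table 25 governs QTc management for patients on both study treatments, including blinded osimertinib/placebo (Table 8 already covers placebo dose reduction). Keep the local-label rule for osimertinib.
2. Align Table 12's Grade 3 trigger and its 80 mg restart condition to Table 25.
3. Add a cross-reference to Table 25 in Tables 20, 21 and 24.
4. Have the sponsor's clinical and cardiac safety team state the intended action when the >60 msec arm fires with QTcF already below 481 msec: either dose reduction without a hold, or a release limit relative to baseline.
5. If a baseline-relative limit is chosen, match the 21-day rule to it. For example, suppose release required both QTcF <481 and a change of 60 msec or less. A patient with baseline 400 who stays at 465 would then not be released (465 > 400 + 60 = 460), and would not be discontinued under the present rule either (465 < 481). The hold would have no written end.

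The cost is a text correction at the next amendment or a clarification letter to sites, with no change to design, sample size or analysis. The downside is a few more holds and so a few more savolitinib restarts, with the hypersensitivity risk that Appendix I 3.4 describes.

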Appendix J Guidance regarding potential interactions with concomitant medications

The use of any permitted concomitant medications must be recorded in the eCRF. Any investigational anti-cancer therapy, concurrent chemotherapy, radiotherapy, immunotherapy, or biologic or hormonal therapy for cancer treatment other than those under investigation in this study must not be given concomitantly while the patient is on study intervention.

Concurrent use of hormones for non-cancer-related conditions (eg, insulin for diabetes and hormone replacement therapy) is acceptable. Local treatment of isolated lesions, excluding target lesions, for palliative intent is acceptable (eg, by local surgery or radiotherapy).

Herbal preparations/medications are not allowed throughout the study. These herbal medications include, but are not limited to: St. John's wort, kava, ephedra (mahuang), gingkobiloba, dehydroepiandrosterone, yohimbe, saw palmetto, and ginseng. Patients should stop using these herbal medications 3 weeks prior to first dose of study drug (3 weeks for St. John's wort).

Based upon studies of in vitro liver microsomes and S9 fractions, savolitinib is metabolised by several metabolic enzymes, including both CYP450 enzymes (CYP3A4, CYP1A2) and some non-CYP enzymes (aldehyde oxidase, UDP-glucuronosyltransferases). Additionally, osimertinib is mainly metabolised by CYP3A4/5.

J 1 Drugs inducing CYP3A4 metabolism that AstraZeneca strongly recommend are not combined with osimertinib or savolitinib

Drug-drug interaction (DDI) studies of osimertinib or savolitinib evaluated in patients showed that there is potential for osimertinib or savolitinib being a victim when co-administered with strong inducers of CYP3A4 (osimertinib or savolitinib concentrations are decreased when co-dosed with rifampicin).

The following potent inducers of CYP3A4 must not be used during this study for any patient receiving osimertinib or savolitinib. Additionally, the use of moderate CYP3A4 inducers may be permitted with caution.

Table 26 Drugs inducing CYP3A4

Strong CYP3A4/5 inducers (should not be combined)	Moderate CYP3A4/5 inducers (permitted with caution)
Avasimibe, carbamazepine, enzalutamide, mitotane, nevirapine, phenobarbital, phenytoin, rifabutin, rifampin, rifapentine, St John's Wort	semagacestat ^a , talviraline ^a , bosentan, efavirenz, etravirine, genistein, lersivirine, lopinavir, modafinil, nafcillin, thioridazine, tipranavir, ritonavir ^b

^a Not available on the US market.

^b Ritonavir has dual effects of simultaneous CYP3A inhibition and induction; the net pharmacokinetic outcome during

chronic ritonavir therapy is inhibition of CYP3A activity.
CYP = Cytochrome P450.

This list is not intended to be exhaustive, and a similar restriction will apply to other agents that are known to be strong inducers of CYP3A4. Appropriate medical judgement is required. Please contact AstraZeneca with any queries you have on this issue.

J 2 Drugs inhibiting CYP1A2 metabolism that AstraZeneca strongly recommend are not combined with savolitinib

Table 27 Drugs inhibiting CYP1A2

Contraindicated drugs	Withdrawal period prior to savolitinib start
Ciprofloxacin, enoxacin, clinafloxacin, fluvoxamine	3 weeks

CYP = Cytochrome P450.

This list is not intended to be exhaustive, and a similar restriction will apply to other agents that are known to strongly inhibit CYP1A2 activity. Appropriate medical judgement is required. Please contact AstraZeneca with any queries you have on this issue.

J 3 Medicines whose exposures may be affected by osimertinib that AstraZeneca considers may be allowed with caution

Osimertinib may increase the concentrations of sensitive breast cancer resistance protein (BCRP) or P-glycoprotein (P-gp) substrate (concentrations of sensitive BCRP substrate, rosuvastatin or P-gp substrate, fexofenadine is increased).

Table 28 Exposure, pharmacological action and toxicity may be increased or decreased by osimertinib

Warning of possible interaction	Advice
Rosuvastatin	Drugs are permitted but caution should be exercised and patients monitored closely for possible drug interactions. Please refer to full prescribing information for all drugs prior to co-administration with osimertinib.
Sulfasalazine	
Doxorubicin	
Daunorubicin	
Topotecan	
Aliskerin	
Dabigatran etexilate	
Digoxin	

J 4 Medicines whose exposures may be affected by savolitinib that AstraZeneca strongly recommend are not combined with savolitinib

Any cytotoxic chemotherapy, investigational agents or other anti cancer drugs for the treatment of advanced NSCLC from a previous treatment regimen or clinical study within 14 days of the first dose of savolitinib should not be combined with savolitinib. Based on in vitro data, savolitinib may be an CCI of CYP2C8, CYP2C9, CYP2D6, and CYP3A4/5. A clinical study with a sensitive CYP3A4 substrate (midazolam) showed no effect when co-dosed with savolitinib and hence, CYP3A4 substrates can be co-dosed with savolitinib.

Savolitinib is a CCI of CYP2C8 (CCI CYP2C9 CCI and CYP2D6 CCI Those drugs defined as CCI CYP2C8, CYP2C9, and CYP2D6 CCI CYP2C8, CYP2C9, and CYP2D6

[please see Table 7 for the example of sensitive substrates]) should be avoided as far as possible during the study unless considered essential by the investigator, in which case patients must be monitored closely for the potential for increased toxicity due to the concomitant medication.

Savolitinib is a substrate of P-gp but unlikely to have clinically relevant effect as the clinical study with itraconazole (a P-gp inhibitor) had no effect on the PK of savolitinib. Savolitinib is a CCI in vitro CCI and hence, drugs that are sensitive substrates of P-gp such as digoxin, quinidine, loperamide, saquinavir and ritonavir should be used with caution. Based on in vitro data, savolitinib is an CCI of OCT2, OATP1B1 and OATP1B3, and clinically significant drug-drug interactions CCI when co-administered with the CCI. Drugs that are known to be significantly affected by CCI activity should be used with caution.

In addition, based on in vitro data savolitinib and CCI may also CCI MATE1, MATE2K, and OAT1/3 leading to an increased chance of a clinically relevant CCI between savolitinib and any co-administered drug that is a substrate for these transporters including metformin. Thus, metformin should be used with caution in case of potential for increased metformin exposure.

In vitro, savolitinib is an CCI of uridine diphospho-glucuronosyltransferase CCI (CCI and hence, sensitive substrates of CCI (such as irinotecan, lamotrigine) should be used with caution.

J 5 Drugs that may prolong QT interval

The drugs listed in this section are taken from information provided by The Arizona Center for Education and Research on Therapeutics website: <https://www.crediblemeds.org>. The website categorises drugs based on the risk of inducing Torsades de Pointes (TdP). During

screening, the drugs that patients are currently prescribed should be checked opposite the Arizona Center website above.

J 5.1 Drugs with a known risk of Torsades de Pointes (TdP)

The following drugs prolong QT interval and are clearly associated with a known risk of TdP even when taken as recommended. These drugs must have been discontinued prior to the start of administration of study treatment, in accordance with guidance provided in [Table 29](#) and should not be co-administered with savolitinib or osimertinib and for a period of one week after discontinuing study treatment.

The list of drugs may not be exhaustive and is subject to change as new information becomes available. As such, investigators are recommended to search the Arizona Center website to confirm the most up to date information. Recommended withdrawal periods following cessation of treatment with these agents are provided in [Table 29](#).

Table 29 Drugs with a known risk of Torsades de Pointes (TdP)

Contraindicated drug	Withdrawal period prior to osimertinib start ^b
Aclarubicin, anagrelide, ciprofloxacin, clarithromycin, cocaine, droperidol, erythromycin, levofloxacin, ondansetron, papaverine hydrochloride, procainamide, sulpiride, sultopride, terfenadine, terlipressin.	2 days
Cilostazol, cisapride, disopyramide, dofetilide, domperidone, flecainide, gatifloxacin, grepafloxacin, ibutilide, moxifloxacin, oxaliplatin, propofol, quinidine, roxithromycin, sevoflurane, sotalol, sparfloxacin, thioridazine	7 days
Bepridil, chlorpromazine, halofantrine, haloperidol, mesoridazine	14 days
Donepezil, terodiline	3 weeks
Levomethadyl, methadone, pimozide	4 weeks
Arsenic trioxide ^a , ibogaine	6 weeks
Pentamidine	8 weeks
Astemizole, probucol, vandetanib	4 months
Amiodarone, chloroquine	1 year

^a Estimated value as pharmacokinetics of arsenic trioxide has not been studied.

^b Values determined from comprehensive review (internal to AstraZeneca) of each compounds pharmacokinetic half-life and determination of the washout period

This list should be checked against the full and most current list presented in the CredibleMeds® website (<https://www.crediblemeds.org/>).

J 5.2 Drugs that may possibly prolong QT interval

The use of the following drugs is permitted (notwithstanding other exclusions and restrictions) provided the patient has been stable on therapy for the periods indicated.

Table 30 Drugs that may prolong QT interval

Drug	Minimum treatment period on medication prior to osimertinib start
Alfuzosin, chloral hydrate, ciprofloxacin, dolasetron, foscarnet, galantamine, gemifloxacin, isridipine, ketoconazole, levofloxacin, mexiletine, nicardipine, octreotide, ofloxacin, ondansetron, quetiapine, ranolazine, telithromycin, tizanidine, vardenafil, venlafaxine, ziprasidone	2 days
Amantadine, amitriptyline, amoxapine, clozapine, doxepin, felbamate, flecainide, fluconazole, fosphenytoin, gatifloxacin, granisetron, imipramine, indapamide, lithium, moexipril/HCTZ, moxifloxacin, risperidone, roxithromycin, sertraline, trimethoprim-sulfa, trimipramine, voriconazole	7 days
Azithromycin, citalopram, clomipramine, itraconazole, nortriptyline, paroxetine, solifenacin, tacrolimus	14 days
Fluoxetine	5 weeks
Protriptyline	6 weeks
Tamoxifen	8 weeks

J 6 References

The Arizona Center for Education and Research on Therapeutics website
Available at URL: <https://www.crediblemeds.org>.

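### Seven drugs barred in Table 29 for known Torsades risk are also permitted in Tables 30 and 7 for patients stable on them, and the only wording on precedence is ambiguous

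*Protocol*

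**What the plan says.** Three places in the protocol govern QT-prolonging co-medication.

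- **Appendix J 5.1 and Table 29** (known Torsades risk). "These drugs must have been discontinued prior to the start of administration of study treatment", and they "should not be co-administered with savolitinib or osimertinib and for a period of one week after discontinuing study treatment". The 2-day withdrawal row begins "Aclarubicin, anagrelide, ciprofloxacin, clarithromycin, cocaine, droperidol, erythromycin, levofloxacin, ondansetron". The 7-day row reads "Cilostazol, cisapride, disopyramide, dofetilide, domperidone, flecainide, gatifloxacin, grepafloxacin, ibutilide, moxifloxacin, oxaliplatin, propofol, quinidine, roxithromycin, sevoflurane, sotalol, sparfloxacin, thioridazine".
- **Appendix J 5.2 and Table 30** (possible QT prolongation). "The use of the following drugs is permitted (notwithstanding other exclusions and restrictions) provided the patient has been stable on therapy for the periods indicated". The periods sit in a column headed "Minimum treatment period on medication prior to osimertinib start". The 2-day row begins "Alfuzosin, chloral hydrate, ciprofloxacin, dolasetron, foscarnet, galantamine, gemifloxacin, isridipine, ketoconazole, levofloxacin, mexiletine, nicardipine, octreotide, ofloxacin, ondansetron", and the 7-day row includes "flecainide, fluconazole, fosphenytoin, gatifloxacin, granisetron, imipramine, indapamide, lithium, moexipril/HCTZ, moxifloxacin, risperidone, roxithromycin".
- **Section 6.5, Table 7.** One row names drugs not to be combined with osimertinib (the do-not-combine row below). The next row repeats the J 5.2 permission and the Table 30 drugs (the permitted row below) and refers to Appendix J, where the periods are given.

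Four eligibility and interaction rules bear on the same drugs. Exclusion criterion 3 in Section 5.2 bars co-medication known both to prolong QT and to cause Torsades. Section 5 allows no exceptions to eligibility. Exclusion criterion 17 bars strong CYP1A2 inhibitors within 3 weeks of the first dose. Table 27 in Appendix J 2 lists ciprofloxacin as contraindicated with savolitinib, with a 3-week withdrawal.

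**The concern.** Table 29 and Table 30 are meant to separate two risk classes: drugs that must be stopped, and drugs that may continue if the patient is established on them. A drug on both lists has two opposite instructions. A site that avoids it complies with every table. A site that relies on the permission breaches J 5.1.

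At stake is patient safety, not inference. Appendix I 3.5 treats QT prolongation as a recognised toxicity of both study drugs. If the permission is taken at its word, a patient could stay on a drug that the protocol itself classes as a known Torsades risk while taking two QT-prolonging study drugs in the combination arms, or one (savolitinib) in the savolitinib + placebo arm.

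**Working it through.** No power, sample-size or error-rate figure is involved, so the check is a comparison of lists and a reading of the precedence wording.

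**Step 1. Count the lists, row by row.**

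- Table 29: 15 + 18 + 5 + 2 + 3 + 2 + 1 + 3 + 2 = 51 drugs.
- Table 30: 22 + 22 + 8 + 1 + 1 + 1 = 55 drugs.
- Table 7, permitted row: the same 55 drugs, apart from one spelling variant (solifenacin).
- Table 7, do-not-combine row: 25 drugs, all of them in Table 29.

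**Step 2. Intersect them.** Table 29 and Table 30 share seven drugs. Table 29 and Table 7's permitted row share the same seven.

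| Drug | Table 29: time off | Table 30: time on | Table 7 permitted row | Table 7 do-not-combine row |
|---|---|---|---|---|
| Ciprofloxacin | 2 days | 2 days | yes | no |
| Levofloxacin | 2 days | 2 days | yes | no |
| Ondansetron | 2 days | 2 days | yes | no |
| Flecainide | 7 days | 7 days | yes | no |
| Gatifloxacin | 7 days | 7 days | yes | no |
| Moxifloxacin | 7 days | 7 days | yes | no |
| Roxithromycin | 7 days | 7 days | yes | no |

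Share of Table 29: 7/51 = 13.7%. No drug in the do-not-combine row is in either permissive list, so Table 7 does not contradict itself drug by drug. The conflict lies between Table 29 on one side and Tables 30 and 7 on the other.

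**Step 3. Can both rules be met while using the drug?** No. Table 29 asks for 2 or 7 days off the drug before osimertinib starts, and Table 30 asks for the same 2 or 7 days on it. Any use that satisfies Table 30 fails Table 29.

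**Step 4. Does any text rank the lists?** Only the bracketed phrase in the permission.

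- In its ordinary sense (*despite*), it lets the permission override Table 29 and exclusion criterion 3.
- If *subject to* was meant, Table 29 and the exclusions prevail, and the seven entries in Table 30 have no effect.

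J 5.1's mandatory wording, exclusion criterion 3 and Section 5 point to the second sense, but none of them says which table governs.

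**Step 5. Ciprofloxacin.** It meets a second, independent bar: Table 27 and exclusion criterion 17, for CYP1A2 inhibition, with 3 weeks off. The literal reading of the permission contradicts that rule too.

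**Step 6. Who could be reached?** Table 30 counts from the start of osimertinib. For most patients that limits the permission to drugs already in use at entry. A savolitinib + placebo patient who crosses over starts study osimertinib after study treatment has begun, so the permission may also reach a drug begun during that period.

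**The case against.** The strongest reply is that this is a list-reconciliation slip behind several safeguards. Exclusion criterion 3 should screen out most such patients, and Section 5 allows no waivers. Appendix J 5 has current prescriptions checked against an external website at screening. Section 6.5 asks for caution and careful monitoring with Table 7 drugs, and Table 7 calls for more frequent ECGs when a drug known to prolong QT is used. Scheduled triplicate ECGs and the QTc management tables follow. The drafters may also have meant *subject to*.

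Much of this stands. It limits exposure and makes widespread misuse unlikely. It does not remove the contradiction. The ECGs and QTc tables detect prolongation; they do not tell a site whether the drug is allowed. The website check points to an outside list and does not rank Tables 29 and 30. By name, Section 6.5 shows the seven only as permitted.

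A second reply is that the documents cannot show which list is right, because a drug's risk class depends on a website that is not part of them. That also stands, and the fix allows for it.

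A reader might go further and count thioridazine (Table 26) and quinidine (Table 7 and Appendix J 4) as additional conflicts, because each is allowed with caution there. The documents do not support this. Those entries concern CYP3A4 induction and P-glycoprotein, and both drugs are already in Table 7's do-not-combine row.

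**Conclusion.** The inconsistency is real and should be fixed. Seven of the 51 drugs in Table 29 (13.7%) are contraindicated in one place and permitted in two others, and the single phrase on precedence is ambiguous, with a literal sense that favours the permission. The count rests only on the printed lists. The number of patients affected is unknown. No efficacy estimate, power or error rate changes.

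Three stronger conclusions that a reader might draw are not supported.

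- *The protocol plainly authorises known-Torsades drugs.* It does not: J 5.1 and exclusion criterion 3 say the opposite, and the permission can be read as subordinate to them.
- *Table 7's allowance for QT-prolonging drugs considered essential must also be overridden.* Removing that route would be a clinical policy decision, not a correction of the overlap.
- *Counts of important protocol deviations will be distorted.* SAP Table 4 includes prohibited medication (6.01), but SAP Section 2.3 refers the full descriptions to a non-compliance handling plan that is not provided, so the effect cannot be verified.

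**What to change.** 1. Delete the seven drugs from Table 30 and from Table 7's permitted row.
2. Add them to Table 7's do-not-combine row, which goes from 25 to 25 + 7 = 32 drugs. That still leaves 51 − 32 = 19 Table 29 drugs unnamed there, so referring the row to Table 29 in full would be cleaner.
3. Replace *notwithstanding* with *subject to* in J 5.2 and in Table 7, so that Tables 27 and 29 and exclusion criteria 3 and 17 prevail.
4. If clinical pharmacology finds that one of the seven no longer carries known Torsades risk, remove it from Table 29 instead. Ciprofloxacin should leave the permissive lists either way, because Table 27 bars it independently.

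The cost is table and wording edits in an amendment or clarification letter, with no change to data or analyses. The downside is that a patient stable on one of these drugs must switch or is ineligible, which exclusion criterion 3 already implies.
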